## **5.3 Secondary Efficacy Analyses**

For secondary efficacy analyses, the observed cases will be used unless stated otherwise.

### **5.3.1 CGI by Physician**

CGI by Physician will be rated at study weeks 2, 4, 6, 8, and 12. Descriptive statistics will be presented by treatment group at each assessment timepoint and for the average of weeks 4 and 6. CGI by Physician will be summarized and analyzed by MMRM, as well as ANCOVA at each assessment timepoint using observed cases. MMRM model will include baseline MAS-B ankle score with knee extended as a covariate and factors of age group, treatment group, visit, treatment-by-visit interaction, study center and previous botulinum toxin exposure. The frequency distribution of the CGI scores, as well as the percentage of responders (CGI score  $\geq 1$ ), will be summarized by treatment group at each post-treatment visit. A logistic regression analysis will also be performed on the responder status at each post-treatment visit with factors of age group, treatment group, study center, and previous botulinum toxin exposure, if applicable.

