7.3.2 Secondary Efficacy Analyses

The observed cases will be used for secondary efficacy analyses unless stated otherwise. CGI by Physician will be rated at study weeks 2, 4, 6, 8 and 12. CGI by Physician will be summarized and analyzed by MMRM as the average of values at weeks 4 and 6 as well as ANCOVA at each assessment timepoint using observed cases. The frequency distribution of the CGI scores, as well as the percentage of responders (CGI score of at least +1), will be summarized by treatment group at each posttreatment timepoint. A logistic regression analysis will also be performed on the responder status at each posttreatment timepoint with factors age group, treatment group, study center, and previous botulinum toxin exposure, if applicable. For GAS by Physician, scores for each of the 2 goals at weeks 8 and 12 will be summarized by treatment group and analyzed by ANCOVA as specified in Section 7.3.1 to assess the treatment differences. For MTS of the ankle of the study lower limb with knee extended and knee flexed, the difference between slow and fast motion (R2 - R1) and the individual R2 and R1 values in degree, as well as the respective changes from baseline, will be summarized by treatment group and analyzed by ANCOVA.

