### **5.2.2                    Other Analyses of Primary Efficacy Variable**

For sensitivity analysis purposes to supplement the primary analyses, an analysis of covariance (ANCOVA) model using MI for missing values will be conducted. A summary of the percentage

of missing MAS-B ankle scores with knee extended by visit will also be provided. The ANCOVA will include baseline MAS-B ankle score with knee extended as a covariate and factors of age group, treatment group, study center and previous botulinum toxin exposure.

The ANCOVA model will be used to analyze each imputation dataset obtained from MI as described in Section 5.1. [REDACTED] will then be used to pool the analyses results across the imputation datasets and produce final parameter estimates. Additional sensitivity analyses for the MAS-B ankle score with knee extended changes from baseline at each assessment time point will also be performed using the same ANCOVA as specified above with observed data, and linear contrasts will be used to estimate the treatment differences between each study dose and placebo.

In addition, the frequency distribution of the grade changes from baseline on the MAS-B ankle score with knee extended, as well as the percentage of responders (with at least a 1-grade reduction in MAS-B), will be summarized by treatment group at each post-treatment office visit. A logistic regression analysis will also be performed on the responder status at each post-treatment visit with a covariate of baseline MAS-B ankle score with knee extended and factors of age group, treatment group, study center, and previous botulinum toxin exposure, if applicable. The additional analyses will be conducted using observed cases unless stated otherwise.

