### Global Attainment Scale by Physician

Each of the 2 goals for each patient at each visit will be analyzed by an ANCOVA model with age group, treatment group, study center and previous botulinum toxin exposure as factors and baseline MAS-B ankle score with knee extended as a covariate to assess treatment differences. The frequency distribution of raw scores for each goal will be summarized by treatment group. Additionally, the percentages of responders who scored 0 or higher (meet or exceed expectation) and the responders who scored -1 or high (slight improvement but not meet expectation) on each functional goal will also be summarized and responder status will be analyzed by logistic regression with factors of age group, treatment group, study center and previous botulinum toxin exposure, if applicable.

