For sensitivity analysis purposes to supplement the co-primary analyses, ANCOVA using MI for missing values will be conducted for the co-primary endpoints of MAS-B ankle score with knee extended and CGI. The model will include baseline MAS-B ankle score with knee extended as a covariate and factors of age group, treatment group, study center, and previous botulinum toxin exposure. A summary of the percentages of missing MAS-B and CGI scores by visit will also be provided. Additional sensitivity analyses for the MAS-B ankle score with knee extended changes from baseline and CGI scores at each assessment timepoint will also be performed using the same ANCOVA with observed data, and linear contrasts will be used to estimate the treatment differences between each study dose and placebo.

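### The CGI and GAS responder models leave out baseline MAS-B, a stratification variable that the matching score analyses include, and give no reason

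*SAP*

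**What the plan says.** Protocol 5.4 and SAP 1.1 stratify randomisation by age group and by baseline MAS-B of the ankle with knee extended (2 versus above 2).

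**Responder models without baseline MAS-B**
- CGI, SAP 5.3.1: logistic regression on the "responder status at each post-treatment visit with factors of age group, treatment group, study center, and previous botulinum toxin exposure, if applicable".
- CGI, Protocol 7.3.2: the regression is "performed on the responder status at each posttreatment timepoint with factors age group, treatment group, study center, and previous botulinum toxin exposure".
- GAS, SAP 5.3.2, for both responder cut-offs: "responder status will be analyzed by logistic regression with factors of age group, treatment group, study center and previous botulinum toxin exposure".

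**Models with baseline MAS-B**
- CGI MMRM, SAP 5.3.1: "MMRM model will include baseline MAS-B ankle score with knee extended as a covariate and factors of age group, treatment group, visit".
- GAS ANCOVA, SAP 5.3.2: the model has "previous botulinum toxin exposure as factors and baseline MAS-B ankle score with knee extended as a covariate to assess treatment differences".
- GAS in Protocol 7.3.2: scores are "summarized by treatment group and analyzed by ANCOVA as specified in Section 7.3.1 to assess the treatment differences", and the Section 7.3.1 ANCOVA contains baseline MAS-B. The Protocol specifies no GAS responder model.
- MAS-B responder model, SAP 5.2.2: "with a covariate of baseline MAS-B ankle score with knee extended and factors of age group, treatment group, study center".
- US FDA CGI ANCOVA, SAP 10.1: "The model will include baseline MAS-B ankle score with knee extended as a covariate and factors of age group, treatment group, study center".

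SAP 5.2.1 says that baseline MAS-B enters the primary MMRM as a continuous variable. Neither document explains why the CGI and GAS responder models drop it.

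**The concern.** The responder models keep the age stratum, centre and prior toxin exposure, so exactly one design variable falls out. A CGI or GAS score analysis and the responder analysis of the same outcome then differ in two ways: the outcome is dichotomised and the adjustment changes. If the two disagree, a reader cannot tell which difference is responsible.

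If baseline MAS-B predicts response, there are two further effects. The odds ratio from the planned model lies closer to 1 than the odds ratio conditional on MAS-B. That is non-collapsibility, a different estimand and not a bias. The planned test also rejects less often under the null than the adjusted test does, because stratified allocation balances a predictor that the model then ignores.

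**Working it through.** **Number of fits.** CGI: weeks 2, 4, 6, 8 and 12, so 5. GAS: 2 goals × 2 cut-offs × 2 visits (weeks 8 and 12) = 8, if fitted by visit as the ANCOVA is. Total 13.

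**The plan's own power figures.** Two-sample t-test, 117 per group, two-sided 0.05, inputs from Protocol 7.5, Table 4:
- MAS-B: difference 0.35, SD 0.75, power 94.5% (stated 94%).
- CGI: difference 0.6, SD 1.2, power 96.8% (stated 97%).
- Product 0.945 × 0.968 = 91.4% (stated at least 91%).

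These reproduce. The documents give no figure for the responder analyses.

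**CGI responder rates implied by Table 4.** Treat CGI as normal, with a rounding cut at 0.5 for a score of at least +1:
- 8 U/kg: Φ((1.2 − 0.5)/1.2) = 72.0%.
- Placebo: Φ((0.6 − 0.5)/1.2) = 53.3%.
- Log odds ratio: ln[(0.720/0.280)/(0.533/0.467)] = 0.81.

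A cut at 1.0 gives 56.6% versus 36.9% and a log odds ratio of 0.80. Table 4 refers to the week 4 and 6 average, so single-visit rates are approximate.

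**Simulation.** Three arms, N = 351, 8 U/kg versus placebo, conditional log odds ratio 0.81.
- From the documents: stratified 1:1:1 allocation; about 30% with MAS-B above 2 (Protocol 5.5); prior toxin exposure 80% at age 6 or below, from the 20% naive target.
- Assumed: blocks of 3; age split 50:50; exposure 90% above age 6; no age or exposure effect on outcome; 20 pooled centres with SD 0.3 on the log-odds scale; 4 U/kg effect 0.7 of the 8 U/kg effect; 3% of patients at score 4.
- Also assumed, and varied: the odds ratio of response per MAS-B grade.

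Both fits contain treatment, age group, exposure and centre; one adds the MAS-B grade. There were 6,000 replicates per setting.

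| Odds ratio per grade | 1 | 0.67 | 0.5 | 0.33 | 0.2 |
|---|---|---|---|---|---|
| Mean log-OR, without | 0.88 | 0.87 | 0.85 | 0.80 | 0.74 |
| Mean log-OR, with | 0.88 | 0.88 | 0.88 | 0.88 | 0.88 |
| Null rejection %, without | 5.8 | 5.8 | 5.5 | 4.8 | 3.7 |
| Null rejection %, with | 5.8 | 6.0 | 5.9 | 5.7 | 5.2 |
| Power %, without | 83.6 | 82.5 | 81.3 | 77.5 | 71.4 |
| Power %, with | 83.6 | 82.8 | 82.3 | 79.6 | 77.2 |
| Nominal gain, points | 0.0 | 0.2 | 1.0 | 2.1 | 5.8 |
| Gain, both tests at 5% size | −0.1 | −0.1 | 0.3 | 0.2 | 0.7 |

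Gains come from unrounded power. The Monte Carlo SE of a 5% rejection rate is √(0.05 × 0.95/6000) = 0.28 points. The excess of 0.88 over 0.81 comes from the centre terms, not from MAS-B. A repeat run gave nominal gains of about 0, 1.6, 2.3 and 5.5 points at odds ratios 1, 0.5, 0.33 and 0.2.

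**Sensitivity** (4,000 replicates per setting)
- 10 centres: nominal gain 0.1 / 0.2 / 1.1 / 2.5 / 6.2; size-matched 0.2 / 0.0 / 0.7 / −0.1 / 1.1.
- Nobody at score 4: nominal 0.5 and 1.6 at odds ratios 0.5 and 0.33; size-matched 0.4 and 0.1.
- 10% at score 4: nominal 2.0 and 4.6 at the same odds ratios; size-matched 0.8 and 2.0.

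**Simpler check.** Two arms, no centre terms, the binary stratum in place of the grade, marginal rates fixed at 72.0% and 53.3%. For an odds ratio of 1, 2, 3 or 5 against response when MAS-B is above 2, the conditional treatment odds ratio is 2.25, 2.30, 2.37 or 2.53. The model without the term targets 2.25 throughout. The power gain runs from 0 to 3.0 points. Null rejection is 4.2 to 4.6% without the term and 4.8 to 5.7% with it.

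**The case against.** The strongest reply is that the numbers hardly favour the change. At equal size the power gain is negligible in the main setting and reaches 2.0 points only if 10% of patients are at score 4. To two decimals, the planned model's mean log odds ratio is never further from 0.81 than the adjusted model's, because attenuation offsets the inflation from the centre terms. At odds ratios of 0.67 to 0.33 the covariate moves null rejection slightly further from 5%. All of this stands, and the case therefore does not rest on power.

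Three further points stand in part.
- The MTS ANCOVA adjusts for baseline MTS instead, so MAS-B is not universal among the secondary models.
- Only the primary MMRM is said to use MAS-B as continuous. For the other models this is inferred, because MAS-B is listed as a covariate apart from the factors.
- The non-FDA CGI ANCOVA in SAP 5.3.1 lists no covariates, so the CGI MMRM is the one explicit comparator there.

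Two possible explanations fail. CGI has no baseline assessment and GAS is scored against preset goals, but the CGI MMRM and GAS ANCOVA adjust for baseline MAS-B all the same. The words if applicable cannot supply a variable that is not listed; they also close the MAS-B responder sentence, where MAS-B is listed.

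Protocol and SAP agree on the CGI responder model. That makes it prespecified, but it is not a rationale.

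**Conclusion.** The concern holds as a low-priority improvement. The gap in the covariate lists is certain from the text; its numerical effect is small and conditional. The documents give no association between baseline MAS-B and CGI or GAS, and with none the gain is nil. Most of the nominal power gain reflects a difference in test size. GAS responder rates are not in the documents, so only CGI was simulated.

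The CGI part concerns the non-US-FDA analyses, on the reading that SAP 10.2 sends the US FDA CGI analyses to 10.1, which lists no CGI responder model. The GAS part applies to both. These analyses are supportive and sit outside the gatekeeping and Hochberg procedures. The benefit is one shared adjustment set for score and responder analyses of the same outcome.

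**What to change.** In SAP 5.3.1 (CGI responders) and SAP 5.3.2 (both GAS responder definitions), specify the model as SAP 5.2.2 does for MAS-B responders, "with a covariate of baseline MAS-B ankle score with knee extended and factors of age group, treatment group, study center", with prior toxin exposure kept. If the omission is intended, one sentence of reasoning in each place is enough. Either step should be taken before unblinding.

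The cost is one degree of freedom per model, for a variable already collected on day 1. The GAS change needs SAP wording only. The CGI model also stands in Protocol 7.3.2, so either that section is amended or SAP Section 12, which now reports no deviations, lists the change.

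The change does not address the inflation from the centre terms, which both versions of the model share.

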### 5.3.2

[figure not shown]
### Global Attainment Scale by Physician

Each of the 2 goals for each patient at each visit will be analyzed by an ANCOVA model with age group, treatment group, study center and previous botulinum toxin exposure as factors and baseline MAS-B ankle score with knee extended as a covariate to assess treatment differences. The frequency distribution of raw scores for each goal will be summarized by treatment group. Additionally, the percentages of responders who scored 0 or higher (meet or exceed expectation) and the responders who scored -1 or high (slight improvement but not meet expectation) on each functional goal will also be summarized and responder status will be analyzed by logistic regression with factors of age group, treatment group, study center and previous botulinum toxin exposure, if applicable.

### 5.3.3

### Modified Tardieu Scale (MTS) of Ankle

The change from baseline of the angle difference, R2-R1, and the individual R1 and R2 respective changes from baseline will be derived at each post-treatment visit and summarized by treatment group, excluding observations where R1>R2. An ANCOVA model with age group, treatment group, study center and previous botulinum toxin exposure as factors and baseline MTS of ankle with knee extended as a covariate will be performed to assess treatment differences. The raw scores of R2-R1, R2 and R1 will also be summarized and analyzed using similar methods. MTS of ankle with knee flexed will be analyzed using the same method as MTS of ankle with knee extended.

## **5.5**

## **Subgroup Analyses for Efficacy Variables**

Subgroup analyses by the stratification factors of age ( $\leq 6$  years and  $> 6$  years), baseline MAS-B score (2 and  $> 2$ ) and previous exposure to botulinum toxin will be performed for primary efficacy variable(s). The “None” subgroup for previous exposure to botulinum toxin is defined as the patients who never received botulinum toxin in the past.

## **6**

## **Safety Analyses**

Safety variables including the incidence of adverse events, the incidence of suicide-related events using the C-SSRS (for patients  $\geq 6$  years of age at day 1), lab tests values and their changes from baseline, as well as vital signs and their change from baseline, immunogenicity tests will be summarized by treatment group using the safety population.

### **6.1**

### **Exposure to Study Treatments**

Patient exposure to the study medication will be characterized by total dose in U, and dose in U/kg body weight.

Duration of follow up is defined as the number of days from the first injection to exit; if the date of exit is missing, the date of the last visit will be used. Data will be summarized with descriptive statistics for each treatment group.

In addition, the total dose in U and dose in U/kg body weight will be summarized by individual muscle, as well as for all muscles combined.

### **6.2**

### **Treatment Emergent Adverse Events**

Adverse events are collected both for the screening/baseline period prior to treatment (which are referred to as pre-treatment adverse events as cited in Section 4.6) and for the follow-up period after treatment is initiated.

A treatment-emergent adverse event (TEAE) is a post-baseline adverse event with onset after the initiation of study treatment or an adverse event with onset prior to study treatment that worsened in severity or became serious after the initiation of study treatment. The number and percentage of patients reporting each event will be summarized and presented for all events and tabulated by treatment groups (8 U/kg, 4 U/kg, and placebo) and overall as follows:

- i. By primary SOC and preferred term. At each level of summarization (overall, primary SOC, and preferred term) a patient will be counted once if he/she reports 1 or more experiences at that level.
- ii. By primary SOC, preferred term and severity. For a given adverse event of a patient, if more than 1 severity grade was reported, the worst severity grade will be included in the tabulation.

All treatment-related TEAEs (study drug-related and injection procedure-related TEAE) will be presented by primary SOC and preferred term. A listing of adverse events leading to discontinuation will also be provided.

The number and percentage of patients with any of the preferred terms will be summarized for each primary SOC and preferred term. All patients will be counted only once for each preferred term when multiple occurrences of the same preferred term are reported.

In addition, individual patient data listings (including adverse event listings that include the investigator verbatim terms and MedDRA lower level terms) will be provided.

Furthermore, the assessment of possible distant spread of toxin will be performed using the list of 39 MedDRA preferred terms (version 19.0 or its updated version as appropriate during the time of data analysis).

MedDRA Preferred Terms Evaluated for Possible Distant Spread of Toxin

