1.3 BOTOX for Management of Pediatric Spasticity

Botulinum neurotoxin type A (BoNT-A) blocks neuromuscular conduction by binding to receptor sites on motor nerve terminals, entering the nerve terminals, and inhibiting the release of acetylcholine. When injected intramuscularly at therapeutic doses, BoNT-A produces localized chemical denervation of the muscle, resulting in focal muscle weakness. This muscle weakness is reversible through nerve ending recovery over a period of 3 or more months. Relaxation of rigid muscles by BoNT-A allows a child to participate in PT or OT, which encourages the use of both targeted and antagonistic muscles with goals of muscle stretching, strengthening, improved motor control, and acquisition of new skills. There has been considerable experience worldwide since the early 1990s with the use of BOTOX in the treatment of spasticity associated with cerebral palsy.

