2.2 Clinical Hypotheses

- 1) A single treatment of BOTOX at doses of 4 U/kg and 8 U/kg in the lower limb has an acceptable safety profile.
- 2) BOTOX with standardized PT is more effective than placebo with standardized PT as measured by a reduction in muscle tone on the MAS-B. For United States (US) Food and Drug Administration (FDA) only, the hypothesis is that BOTOX with standardized PT is more effective than placebo with standardized PT as measured by a reduction in muscle tone on the MAS-B and improvement on the Clinical Global Impression of Overall Change (CGI) by Physician.

3. Study Design

This is a multicenter, randomized, double-blind, placebo-controlled, parallel-group, 12-week study evaluating 2 doses of BOTOX, 4 and 8 U/kg, and placebo with standardized PT for the treatment of spasticity involving the ankle plantar flexors in monoplegic and hemiplegic children. Patients who successfully complete this study without major protocol deviations (eg, noncompliance to protocol-required procedures) will be given the option of enrolling in the open-label extension Study 191622-112 if they meet eligibility criteria.

The maximum study duration per patient will be approximately 16 weeks (including up to 4 weeks in the screening period). Patients will complete 8 study visits as follows: screening (week -4 to week -2), initiation of standardized PT (week -2), randomization and treatment visit (day 1), and post-injection follow-up visits at weeks 2, 4, 6, 8, and 12.

There will be 1 treatment cycle in the study. Only 1 affected lower limb (referred to as the study limb) will be treated. Patients will be randomized in a 1:1:1 ratio to one of the

following treatment groups: 4 U/kg (not to exceed 150 U) + PT, 8 U/kg (not to exceed 300 U) + PT, or placebo + PT.

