7.3.4 Safety Analyses

Safety variables, including the incidence of adverse events, the incidence of suicide-related events using the C-SSRS (for patients \geq 6 years of age at day 1), laboratory test values and changes from baseline, as well as vital signs and their change from baseline, will be summarized by treatment group using the safety population. The Medical Dictionary for Regulatory Activities (MedDRA) nomenclature will be used to code adverse events and medical history. The incidence of adverse events (both pretreatment events and treatment-emergent events) will be tabulated by primary system organ class and preferred term for each treatment group. Possible distant spread of toxin adverse events will be assessed using a standardized methodology.

Descriptive statistics will be presented for vital signs and numeric laboratory tests and the respective changes from baseline. All laboratory values will be presented by descriptive statistics. In addition, laboratory values outside the normal reference ranges for each patient at each applicable visit will be identified and evaluated against baseline via shift table analysis. Potentially clinically significant abnormal values may be identified or summarized descriptively.

Immunogenicity results for each patient will be reported as positive, negative, or inconclusive. Correlations between immunogenicity results and other variables may be performed if warranted.

Approval Date: 25-Jul-2016

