**Musculoskeletal and Connective Tissue Disorders**

Muscular weakness

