**Nervous System Disorders**

Bulbar palsy  
Cranial nerve palsies multiple  
Cranial nerve paralysis  
Dysarthria  
Facial paralysis  
Facial paresis  
Hyporeflexia  
Hypotonia  
Paralysis  
Paresis cranial nerve  
Peripheral nerve palsy  
Peripheral paralysis  
Speech disorder  
Vocal cord paralysis  
Vocal cord paresis

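### SAP 6.2 assesses possible distant spread of toxin from a preferred-term list with no location or review step, so injected-calf weakness or hypotonia reported as an adverse event would be flagged together with remote events

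*SAP*

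**What the plan says.** Protocol Section 7.3.4 gives the principle only: "Possible distant spread of toxin adverse events will be assessed using a standardized methodology". It does not describe the method.

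SAP Section 6.2 supplies the one operational detail: "the assessment of possible distant spread of toxin will be performed using the list of 39 MedDRA preferred terms". The list follows under the title "MedDRA Preferred Terms Evaluated for Possible Distant Spread of Toxin", grouped by system organ class. It includes "Muscular weakness" under musculoskeletal disorders, and Hypotonia and "Hyporeflexia" under nervous system disorders. None of these three carries a site.

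On what the drug does where it is injected, Protocol Section 1.3 states that "BoNT-A produces localized chemical denervation of the muscle, resulting in focal muscle weakness". The efficacy hypothesis in Protocol Section 2.2 is framed "as measured by a reduction in muscle tone on the MAS-B". Protocol Section 5.6.1.1 places all injections in the gastrocnemius, soleus and tibialis posterior of the study limb.

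SAP Section 6.2 also plans tables of all treatment-emergent events by preferred term and treatment group, and patient listings with verbatim and lower level terms. It does not link those listings to the distant-spread assessment.

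**The concern.** A preferred term such as Muscular weakness does not record which limb was weak. A child reported with a weak injected calf and a child reported with weak arms receive the same code and match the same entry on the list. The first is an exaggerated form of the drug's local action. The second is the kind of event the assessment exists to find. The plan gives no step that separates them.

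Two errors could follow. Local effect plausibly rises from placebo through 4 U/kg to 8 U/kg, so local events alone could look like a dose-related pattern of distant spread. In the other direction, a few true remote events could be diluted by local ones and be harder to see in a grouped count. Safety at both doses is the first clinical hypothesis in Protocol Section 2.2, and distant spread is the only adverse-event topic with its own term list in SAP Section 6.2.

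Timing also matters. Protocol Section 7 places the planned analyses after database lock and release of the randomization data. If location is first considered then, the sorting could be done with treatment known.

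**Working it through.** **1. Reproduce the plan's own figure.** Counting the printed terms by system organ class (SAP Section 6.2):

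- Cardiac 1, eye 7, gastrointestinal 4, infections 1, musculoskeletal 1, nervous system 15, renal and urinary 1, respiratory 8, reproductive 1.
- 1 + 7 + 4 + 1 + 1 + 15 + 1 + 8 + 1 = 39, all distinct.

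This agrees with the stated 39, so the list is complete as printed.

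**2. Which terms can describe a local effect in the calf.**

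- Many terms could not refer to the calf, because they name another site or function: Eyelid ptosis, Facial paresis, Vocal cord paralysis, Diaphragmatic paralysis and Pelvic floor muscle weakness are examples.
- Muscular weakness and Hypotonia name no site and match what the protocol expects at the injected muscle (focal weakness in Section 1.3, lower tone in Section 2.2). Share of the list: 2/39 = 5.1%.
- Hyporeflexia, Paralysis, Peripheral paralysis and Peripheral nerve palsy do not place the event in a particular limb either. The documents do not describe them as local effects of the drug, so they are included only as a precaution. With these the share is 6/39 = 15.4%.

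These are shares of the list, not of events. The point rests on the first two terms.

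**3. Look for a rule on location.** Set side by side:

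- Protocol Section 7.3.4 refers to a standardized method without content.
- SAP Section 6.2 gives the list and nothing after it: no site criterion, no medical review or adjudication, and no description of the table or listing to be produced.
- SAP Section 6.2 separately lists verbatim terms, which may state a site, but assigns them no role here.
- SAP Section 12 reports no deviations from Protocol Amendment 3, so no extra step enters there.

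On the text as written, a match on the term is the only criterion.

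**4. How a local effect gets into the data.** Protocol Section 9.1.1 limits adverse events to untoward occurrences. A lower MAS-B score is an efficacy result and does not become an adverse event through that score. The same section allows for unfavorable signs and symptoms and for directed questioning and examination at visits. Section 8.3.5 adds a physical examination at exit, which Section 12.1.1 extends to neurologic, extremity and musculoskeletal findings. A report of excess weakness in the injected calf is therefore plausible, though not automatic.

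**5. Size, as an illustration only.** The documents give no rate of local weakness or hypotonia reported as an adverse event, so the rates below are assumptions.

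- Patients per arm: 412/3 = 137.3, about 137 (enrolment target in Protocol Section 7.5, 1:1:1 allocation).
- Patients flagged for local events = 137 × assumed rate.

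| Assumed rate | Patients per arm |
|---|---|
| 1% | 137 × 0.01 = 1.4 |
| 3% | 137 × 0.03 = 4.1 |
| 5% | 137 × 0.05 = 6.9 |
| 10% | 137 × 0.10 = 13.7 |

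The range is about 1 to 14 patients per arm. If, for example, the rate were 1% on placebo, 3% on 4 U/kg and 5% on 8 U/kg, local events alone would put about 1, 4 and 7 patients among the matches. That gradient is put in by assumption. It shows that the mechanism can produce a pattern, not that it will.

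**The case against.** The best reply is that the list is a search tool and not a classification. Its title speaks of terms evaluated for possible spread, and the protocol's standardized method may include a case review that is not set out here. A reader might infer from SAP Section 6.2 that every report of weakness, low tone or reduced reflexes is counted as distant spread wherever it occurs, and that the drug's intended effect is therefore tabulated as a harm. The documents do not support that. They do not say what is done with a match or what output results. The intended effect enters only if an investigator reports it as untoward. Hyporeflexia is nowhere described as a local effect. This part of the reply stands, and it limits the point to what the written rule would flag.

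A second reply is that other planned outputs reduce the harm. The tables by preferred term would show whether an excess came from Muscular weakness or from, say, Dysphagia, and the listings would reveal a remote case whose verbatim term names a site. This also stands in part. Those tables still cannot divide Muscular weakness by limb, and reading the listings after unblinding is not a pre-specified assessment.

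Third, this is a descriptive summary with no stated test or decision rule, and it does not touch the efficacy conclusions. That is true and bears on priority. It does not remove the gap: a search list needs a stated next step. If a review step already exists, writing it into SAP Section 6.2 settles the matter; if not, one is needed before lock.

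**Conclusion.** The point holds in a limited form. SAP Section 6.2 defines the distant-spread assessment by preferred term alone and states no location or review step. Muscular weakness and Hypotonia are on the list without a site and match the drug's stated action at the injected muscle, so calf events reported as adverse events would be flagged together with remote ones.

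The size is unknown. The range of about 1 to 14 patients per arm depends wholly on assumed rates of 1% to 10% and on about 137 patients per arm. The possible resemblance to dose-related spread rests on the assumption that reported local effect rises with dose, which is plausible but not quantified in the documents. The assessment is not worthless: most of the 39 terms are outside the problem, and the planned tables and listings allow some disentangling. This is a cheap improvement to a safety summary, best made before database lock.

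**What to change.** In SAP Section 6.2:

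1. Keep the 39-term search and report its unsplit total by treatment group, so that no match is removed and comparison with other studies remains possible.
2. For Muscular weakness and Hypotonia, and as a precaution Hyporeflexia, Paralysis, Peripheral paralysis and Peripheral nerve palsy, add a split by treatment group into two rows: confined to the injected limb, and outside the injected limb or site not stated.
3. Assign the row from the investigator's verbatim term, under blind and before database lock, and record the assignment.
4. For these six terms, base the interpretation of distant spread on the second row, read together with the remaining listed terms and the unsplit total.

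The cost is a short addition to the SAP and a brief blinded review of verbatim terms already collected. It needs no new data and changes no study procedure. The downside is that local events whose verbatim term names no site stay in the second row, so the separation will be incomplete. That error is on the cautious side.
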